## **Hypothesis**

### **Primary:**

Curing the exit site of the indwelling hemodialysis catheter with 2% self-adhesive chlorhexidine gluconate semi-permeable polyurethane dressings (AGC) will correlate with a lower incidence of catheter-related infections (bacteremia, exit site infection, and tunnelitis), than healing with chlorhexidine in 2% aqueous solution and covered with a dressing of self-adhesive semi-permeable polyurethane dressings.

### **Secondary:**

- The degree of comorbidity, previous infections, time on renal replacement therapy, and catheter duration will correlate with a higher rate of catheter-related infections.
- Hemodialysis catheter exit site dressing with AGC dressings will correlate with higher patient satisfaction than dressing with 2% chlorhexidine solution and covered with a self-adhesive semi-permeable polyurethane dressing.

## **Objectives**

### **Main:**

To compare the rate of catheter-related infections (bacteremia, exit site infection and tunnelitis) between hemodialysis catheter exit site dressing with self-adhesive ACG dressings and dressing with 2% chlorhexidine solution and covered with self-adhesive semi-permeable polyurethane dressing.

### **Secondary:**

- To evaluate factors related to the incidence of hemodialysis catheter-related infections.
- To evaluate the incidence of dressing-related skin alterations.
- To assess patient satisfaction with regard to the type of hemodialysis catheter exit site dressing.

## **Methodology**

**Design:** Experimental, controlled and randomized study. Patients will be randomized from sealed envelopes. These envelopes will contain the outflow orifice treatment group to which each patient will be assigned. The envelopes will be numbered and the patients will be included consecutively. The contents of the envelopes will be made by a person outside the research team. A member of the research team will invite the patient to participate in the study, informing him/her of the details of the study orally and in writing (see patient information sheet), after his/her acceptance and signature of the informed consent, the patient will be randomized. Duration: November 2020 to December 2022.

### **Intervention:**

- Cure guideline control group- cleansing exit orifice with physiological saline (0.9%), drying with sterile gauze, disinfection with 2% water-based chlorhexidine solution, environmental drying for 30 seconds and covering with self-adhesive semi-permeable polyurethane dressing.
- Cure guideline experimental group - cleaning of the exit orifice with physiological saline (0.9%), drying with sterile gauze, application of a semi-permeable polyurethane dressing with 2% self-adhesive chlorhexidine gluconate, centering the chlorhexidine gluconate band well in the exit orifice.

Outflow orifice curettage will be performed by experienced nurses from our hemodialysis unit, after a briefing on the study methodology. In both cases the treatment will be performed weekly (first day of the week), or whenever there is exudate from the exit site or detachment of the dressing; before connecting the catheter to the hemodialysis monitor. In both cases, the treatment will be carried out under maximum aseptic measures: previous hand hygiene, sterile material and treatment, and use of masks by the patient, nurse and nursing assistant. The connection to the hemodialysis monitor will be performed under these aseptic measures, covering the connection between the lines and the catheter with gauze impregnated with 2% water-based chlorhexidine solution and a sterile cloth. In addition, a bioconnector is used for hemodialysis catheters.

**Population:** patients on renal replacement therapy with hemodialysis whose vascular access is an indwelling catheter. Fifty patients will be included (25 patients in the control group - chlorhexidine 2% solution and covered with self-adhesive transparent polyurethane dressing - and 25 patients in the experimental group - with self-adhesive ACG dressings). The sample size calculation was performed with the GRANMO program version 7.12, accepting an alpha risk of 0.05 and a beta risk of 0.2 in a bilateral contrast, to detect as statistically significant the difference between two proportions, which for the control group is expected to be 25% and the experimental group 5%. A loss-to-follow-up rate of 10% has been estimated.

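### The planned 50 patients in total are at most half of what the plan's own assumptions require, so power is roughly 35–56%, not the stated 80%

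*Combined protocol and SAP*

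**What the plan says.** The sample size is in the Population paragraph, under Intervention in the Methodology. The allocation is explicit: "Fifty patients will be included (25 patients in the control group" and "and 25 patients in the experimental group - with self-adhesive ACG dressings". The total is therefore 50, and it cannot be read as 50 per arm.

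The same paragraph names GRANMO 7.12 as the software. It gives the error rates as follows: "accepting an alpha risk of 0.05 and a beta risk of 0.2 in a bilateral contrast". The target is a difference between two proportions, 25% in the control group and 5% in the experimental group. On attrition it says: "A loss-to-follow-up rate of 10% has been estimated". It does not say which variance formula the program used.

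The section on data collection and analysis compares categorical variables by chi-square, or by Fisher's exact test where needed, at p<0.05. The limitations section names only the three-month follow-up.

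**The concern.** Every input to the calculation is stated, so the result can be checked, and 25 per group looks far too small. A fall from 25% to 5% is large, but both proportions are low. With 25 per arm the plan expects 6.25 infected control patients and 1.25 infected experimental patients, 7.5 in all.

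The beta of 0.2 is the protocol's only statement of its chance of detecting the hypothesised effect. If it is wrong, a non-significant result could be read as the negative finding of an 80%-powered trial when it was about as likely as not even with the dressing working as hoped. Nothing in the limitations section corrects that reading.

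**Working it through.** **Inputs** (all from the Population paragraph): p1 = 0.25, p2 = 0.05, difference d = 0.20, mean proportion 0.15; two-sided alpha 0.05 (z = 1.960); beta 0.2 (z = 0.8416); (1.960 + 0.8416)² = 7.849; equal allocation; loss 10%, applied by dividing by 0.9.

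**Can 25 per group be reproduced?** Required size per group:

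- Arcsine: 7.849 / [2 × (asin√0.25 − asin√0.05)²] = 7.849 / (2 × 0.2981²) = 44.17.
- Unpooled: 7.849 × (0.25×0.75 + 0.05×0.95) / 0.20² = 7.849 × 0.235 / 0.04 = 46.1.
- Pooled: [1.960 × √(2×0.15×0.85) + 0.8416 × √0.235]² / 0.04 = 48.8.
- Pooled with continuity correction: (48.84/4) × [1 + √(1 + 4/(48.84×0.20))]² = 58.4.

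| Formula (two-sided) | Per group, evaluable | Per group after loss | Total |
|---|---|---|---|
| Arcsine | 45 | 45/0.9 = 50 | 100 |
| Unpooled | 47 | 53 | 106 |
| Pooled | 49 | 55 | 110 |
| Continuity-corrected | 59 | 66 | 132 |

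None gives 25. A one-sided test, which the text rules out, still needs 35 to 48 per group before loss. A one-sample comparison with a fixed 25% comes near (27 two-sided before loss), but that is not the two-group design described.

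**Power for 25% versus 5% at the planned size.** A 10% loss from 25 leaves 22.5 per arm, so 22 or 23.

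| Method | 25 per arm | 22 per arm | 23 per arm |
|---|---|---|---|
| Pooled normal | 50.8% | 45.8% | 47.5% |
| Arcsine | 55.9% | 50.7% | 52.5% |
| Uncorrected chi-square, exact enumeration | 55.5% | 49.1% | 51.3% |
| Fisher's exact, exact enumeration | 37.0% | 34.9% | 37.3% |

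Fisher's test moves in steps at these sizes. With unequal arms its power is 38.5% for 23 control and 22 experimental patients, and 47.8% for 22 and 23.

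**Which test is likely?** Under no difference, 7.5 expected infections split as 3.75 per arm. That is below the customary threshold of 5, which points to Fisher. The outcome closest to the hypothesis in whole patients, 6/25 versus 1/25, gives Fisher p = 0.098. It takes 7/25 versus 1/25 to reach p = 0.049.

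**What would have 80% power?** Against 5% in the experimental arm, 25 per arm needs a control proportion of about 34% (arcsine), 36.5% (pooled) or 39% (Fisher). With 22 per arm the figures are about 36.5%, 39.5% and 41.5%.

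**The case against.** Four points can be made for the plan; none restores the stated 80%.

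- **The required size depends on the formula.** The plan names the software but not the formula, and its output is not shown. This stands: 100 is the low end of a range up to 132, and nobody can say from the documents which figure the program returned. But every standard two-sided version needs at least twice the planned number.
- **The cause is not documented.** 45/0.9 = 50 per group suggests a per-group result taken as the total, but that is inference. The discrepancy does not depend on it.
- **The power figure depends on test and loss.** With complete follow-up, the arcsine approximation and the uncorrected chi-square give about 56%. Approximate values near or below 50% need the pooled formula or the planned loss. The plan also sets no threshold for switching to Fisher; the limit of 5 is convention, so the lower figures are conditional on it.
- **Resources are acknowledged.** The limitations section mentions scarce funds for dressings, but only to explain the short follow-up. It does not disclose low power.

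The plan also defines an infection rate per 1,000 days of follow-up. That is a separate matter, because the calculation is expressly for two proportions.

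**Conclusion.** The concern holds. The stated inputs require at least 50 patients per group after loss (100 in total, and up to 132 depending on the formula), against 25 per group planned.

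The real type II error is about 0.44 to 0.65 (power 56% down to 35%) instead of 0.2. Once the plan's own 10% loss is counted, power is about 50% or less: 46–52% by approximation and 35–48% with Fisher.

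These figures assume equal allocation, the plan's 25% and 5%, and analysis as a simple comparison of two proportions. The Fisher figures further assume the usual expected-count convention. The statement of 80% power is wrong as written and must be corrected.

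**What to change.** Rewrite the sample-size paragraph in one of two ways.

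1. **Restate the power and keep 50 patients.** Withdraw the beta of 0.2. State that 25 per arm, with 22–23 evaluable, gives about 50% power for 25% versus 5%, and about 35–48% if Fisher's exact test is used. State that 80% power exists only for control proportions of roughly 34–42% against 5%, depending on test and loss. Add the shortfall to the limitations section.
2. **Correct the number.** Rerun the calculation, name the formula, and report the per-group and total size before and after loss. On the stated inputs the total will be at least 100.

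Under the first option it would also be sensible, though not part of the arithmetic correction, to report the treatment effect with its 95% confidence interval as the main result and to say that non-significance is not evidence of no effect.

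The first option costs only wording and a less favourable power figure. The second at least doubles recruitment and is not needed to make the document correct.

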#### **Inclusion criteria:**

- Be included in hemodialysis program in our unit.
- Be a carrier of a catheter as vascular access, inserted 1 month prior to inclusion in the study.
- Remain on hemodialysis treatment for at least 3 months at the dialysis center
- Consent to participate in the study.

#### **Exclusion criteria:**

- Allergy or hypersensitivity to chlorhexidine or polyurethane dressing
- Use of a non-tunneled venous catheter as vascular access.
- Active catheter-related infection at the time of inclusion in the study.

#### **Causes of patient loss:**

- Exitus.
- Renal transplantation
- Use of arteriovenous fistula as vascular access.
- Transfer to peritoneal dialysis program.
- Hypersensitivity reaction to chlorhexidine gluconate.
- Exit from hemodialysis program due to other clinical situations.

**Follow-up period:** Patients carrying an indwelling catheter: 3 months.

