#### **Variables:**

- a) **Patient clinical variables**- age, sex, etiology of renal disease according to ERA/EDTA code, degree of comorbidity according to the modified Charlson Index for patients with renal disease, time on renal replacement therapy with hemodialysis.
- b) **Catheter affiliation variables** - design (twin or single), material (carbonate or polyurethane), date of insertion, date of removal, vein of insertion, previous catheter-related infections (bacteremia, tunnelitis, exit site infection).

c) **Catheter-related infections** during the follow-up period- will be defined as:

- *Bacteremia*- presence of fever (body temperature  $\geq 38^{\circ}\text{C}$ ) along with a positive blood culture, with no other focus of infection.
- *Exit site infection*- positive culture of pericatheter smear together with presence of inflammatory signs limited to 2 cm around the cutaneous exit site, with no upper extension to the catheter cuff if tunneled.
- *Tunnelitis*- appearance of inflammatory signs extending beyond 2 cm from the cutaneous exit site and in the subcutaneous tract of the catheter (tunnelitis). It may or may not be associated with fever and bacteremia, and may be accompanied by purulent exudate through the cutaneous exit site.

In case of clinical suspicion of bateremia due to fever (body temperature  $\geq 38^{\circ}\text{C}$ ), 2 blood cultures will be taken 30 minutes apart, from aerobic and anaerobic germs, directly from the arterial branch of the catheter.

The exit orifice will be inspected at each dressing, and the nurse in charge will take a photograph of it before performing the dressing, to check for the presence of signs of infection by the investigating team. In the presence of signs of infection, a culture of the pericatheter smear will be taken before the exit site is cured.

d) **Patient satisfaction** with the treatment regimen. - Patients will be surveyed after the follow-up period of the study about discomfort related to the type of treatment: pain on withdrawal, presence of pruritus, loss of adherence, alteration of body image, degree of comfort. To assess these aspects, SCALE 18 Degree of perception of positive expectations, of the NOC taxonomy (5-point Likert-type scale where 1- Not at all satisfied, 2- Somewhat satisfied, 3- Moderately satisfied, 4- Very satisfied, 5- Completely satisfied) will be used.

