e) Incidence of dressing-related skin alterations. - will be assessed at each hemodialysis session, using the following NOCs:

- [110115] Skin lesions
- [110121] Erythema

SCALE 14 Degree of a negative or adverse condition or response (Severe - Substantial - Moderate - Mild - None)

**Data collection and analysis:** An Excel-type data collection sheet will be created with the variables to be studied. The variables will be introduced by a member of the research team and will be extracted from the patients' clinical records (clinical reports, dialysis evolution sheets, catheter evolution sheets and analytical results). The survey of satisfaction with the treatment will be carried out by a member of the research team at the end of the follow-up period.

A descriptive analysis of the variables under study will be performed: in the case of quantitative variables, measures of central tendency and dispersion appropriate to the distribution and their 95% confidence intervals will be calculated; in the case of categorical variables, the frequency and percentage will be calculated. The catheter-related infection rate (bacteremia, exit site infection and tunnelitis) will be calculated using the following formula: number of catheter-related infections/ days of follow-up  $\times 1000$ ; both for the total number and by intervention group and type of catheter. In the case of comparisons between categorical variables, the chi-square test or Fisher's exact test will be used when necessary. Continuous variables will be compared using Student's t-test or Mann Whitney U-test, depending on their distribution. For the study of variables associated with the presence of catheter-related infections, a multiple logistic regression analysis will be performed including as independent variables age, sex, etiology of renal disease, degree of comorbidity, time on renal replacement therapy with hemodialysis,

type and model of catheter, duration of the catheter, location, and presence of previous catheter-related infections. The results will be considered significant if the critical level observed is less than 5% ( $p<0.05$ ). Statistical analysis will be performed with the PSPP statistical package.

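### A chlorhexidine reaction during the study counts as patient loss, although a patient who keeps the catheter can still be followed for infection and surveyed

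*Combined protocol and SAP*

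**What the plan says.** - **Exclusion criteria** bar patients with "Allergy or hypersensitivity to chlorhexidine or polyurethane dressing".
- **Causes of patient loss** has six items. Five are death, transplantation, a switch to a fistula, transfer to peritoneal dialysis and leaving hemodialysis for other clinical reasons. The sixth is "Hypersensitivity reaction to chlorhexidine gluconate", with no restriction to one arm.
- **Follow-up period**, directly after that list, reads: "Patients carrying an indwelling catheter: 3 months".
- **Population** allows 10% for losses, in the sense of patients lost to follow-up.
- **Variables, item c**: infections count if they occur during follow-up. For exit-site infection, "The exit orifice will be inspected at each dressing", with a photograph each time and a smear if there are signs of infection.
- **Variables, item d**: "Patients will be surveyed after the follow-up period of the study about discomfort related to the type of treatment". **Data collection and analysis** adds that the survey is "carried out by a member of the research team at the end of the follow-up period".
- **Variables, item e**: skin lesions and erythema, by contrast, "will be assessed at each hemodialysis session".
- **Data collection and analysis** gives an infection rate per 1,000 days of follow-up, and also provides: "In the case of comparisons between categorical variables, the chi-square test" or Fisher's exact test. A logistic model is planned for the presence of infection.

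No section says what happens to data after a reaction, which patients are analysed, or how missing outcomes are handled.

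**The concern.** Five of the six listed causes remove the patient from hemodialysis through the catheter, so the infection outcome can no longer be observed. A reaction does not do this by itself, and nothing in the protocol says that the catheter is then removed. The patient may go on attending the same unit with the same catheter, at continuing risk of infection.

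Chlorhexidine is also the agent under study. The control arm has it applied as a solution, the experimental arm wears it in the dressing, and both arms have it on the gauze at the line connection. Form and contact time differ, so equal reaction rates cannot be presumed. Losses of this kind could therefore differ by arm and could be linked to outcome. They are also avoidable.

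Three results are exposed: infections after the reaction, any yes/no infection analysis that ignores follow-up time, and satisfaction. Patients who react may be those with most to report on pruritus and comfort, both of which are survey items.

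**Working it through.** **Reading the passages together**

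1. Known allergy is excluded at entry, so the loss item concerns reactions during the study.
2. Follow-up is tied to carrying the catheter for 3 months. A patient who reacts and keeps the catheter meets this definition and is also on the loss list.
3. The list does not say in words that recording stops. The sample-size text uses loss to mean loss to follow-up, so that is the natural reading.
4. Skin grading at each session is unaffected up to the loss. The rate per days of follow-up uses time up to the loss, so it stays unbiased only if later infection risk is unrelated to the reaction. That cannot be checked once recording stops.
5. The survey could be given at the end of each patient's own follow-up, but no survey at departure is clearly planned.

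**Illustrative size**

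The plan gives no figure for this point, so there is none to reproduce.

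- From the documents: 25 patients per arm; planned infected proportions of 25% (control) and 5% (experimental); loss allowance 10% × 25 = 2.5 patients per arm.
- Assumed: k = 0, 1 or 2 reactions in an arm (two is within the 2.5 allowance); 3 months = 90 days; the planned proportions are 3-month risks spread evenly over time; each reaction is on day 30, leaving 60 days unobserved.
- Patient-days per arm: 25 × 90 = 2,250.
- Unseen risk per patient who reacts: 25% × 60/90 = 16.7% at the control risk; 5% × 60/90 = 3.3% at the experimental risk.

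| Quantity | Formula | k = 0 | k = 1 | k = 2 |
|---|---|---|---|---|
| Share of arm unsurveyed, if no survey at departure | k/25 | 0% | 4% | 8% |
| Patient-days unobserved | 60k/2,250 | 0% | 2.7% | 5.3% |
| Expected unseen infected proportion, control (points) | k × 16.7%/25 | 0 | 0.67 | 1.33 |
| Same, experimental (points) | k × 3.3%/25 | 0 | 0.13 | 0.27 |
| Bound if every such patient were infected unseen (points) | k/25 | 0 | 4 | 8 |
| Chance of at least one unseen infection, control risk | 1 − (1 − 0.1667)^k | 0% | 16.7% | 30.6% |
| Same, experimental risk | 1 − (1 − 0.0333)^k | 0% | 3.3% | 6.6% |

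The planned difference is 25% − 5% = 20 points.

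**Sensitivity to the reaction day** (k = 2, control risk)

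- Day 7: 25% × 83/90 = 23.1%, so 1 − (1 − 0.231)² = 41%.
- Day 60: 25% × 30/90 = 8.3%, so 1 − (1 − 0.083)² = 16%.

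**On the rate scale**, with full follow-up and one infection per infected patient:

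- Control: 6.25/2,250 × 1,000 = 2.78 per 1,000 days.
- Experimental: 1.25/2,250 × 1,000 = 0.56 per 1,000 days.
- One infection: 1/2,250 × 1,000 = 0.44 per 1,000 days. If the 60 missing days are restored with it, the control rate moves from 6/2,190 (2.74) to 7/2,250 (3.11), a change of 0.37.

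**Effect of one missed infection on Fisher's test** (chosen counts, one experimental patient lost)

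- Near the planned proportions: 6/25 v 1/24 gives p = 0.098. With the missed infection counted, 6/25 v 2/25 gives p = 0.247. Neither is significant.
- With more control infections than planned (8/25 = 32%): 8/25 v 1/24 gives p = 0.023, and 8/25 v 2/25 gives p = 0.074.

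**The case against.** The strongest reply is that loss is never defined for data purposes. Variables are taken from clinical, dialysis and catheter records, which continue while the patient stays in the unit, and blood cultures are triggered by fever, not by the assigned dressing. Bacteremia at least could still be captured. **This stands in part:** later retrieval is possible, but it is not planned, and finding exit-site infection depends on inspection, photograph and smear at dressing changes.

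The main objective compares a rate per days of follow-up, so early exit shortens the denominator. With constant risk unrelated to the reaction, the expected bias in that rate is zero. **This stands**, subject to an assumption that cannot be tested without later data. The protocol also never names the yes/no comparison as the primary test, although its sample size is based on two proportions.

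Stopping observation when the assigned product can no longer be used could be a deliberate on-treatment choice. **That is a legitimate question to ask, but not one the plan makes**, and its own follow-up definition points the other way.

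Finally, the numbers are small and assumed. The day-30 assumption matters (16% to 41% across days 60 to 7), two reactions would use nearly the whole loss allowance on one cause, and the significance change appears only with chosen counts. **All of this stands** and limits the size of the point. It does not remove the conflict between the loss list and the follow-up definition.

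**Conclusion.** The concern holds. Followed as written, the loss list can drop patients who still meet the plan's follow-up definition, for a reason that may be related to the assigned treatment. This is a stated rule with a risk of bias, not merely a missing detail. Neither size nor direction can be estimated, and the effect may be zero. Under the assumptions used, the expected distortion of the infected proportion is small, but with only 6.25 + 1.25 = 7.5 infected patients expected in the whole trial, a single unrecorded infection can matter. Confidence is medium, because it rests on reading loss as the end of recording. The change is worth making because it is cheap.

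**What to change.** 1. Remove hypersensitivity as a reason to end data collection, and leave its clinical handling as it is. Keep recording infections to 3 months in the assigned group while the patient remains in the unit with the catheter, using the same inspection, photograph and smear where feasible.
2. Give the satisfaction survey at departure, or when the assigned dressing is discontinued, to everyone who can be surveyed.
3. Analyse all randomised patients in their assigned group, counting infections and days up to any true departure. Report hypersensitivity and losses by cause and arm.

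**Cost:** protocol wording, a few earlier surveys, and some extra exit-site recording after a reaction, since clinical records alone would not guarantee equal detection of exit-site infection. **Downside:** some dilution of the infection effect, because these patients may be on neither trial regimen after the reaction.
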